7.2 Methods

A pre-operative screening visit (or multiple visits if required) will be conducted to ensure eligibility for enrollment and will typically occur as part of routine clinical assessment at each of the participating centers.

A pre-operative interview (as part of the informed consent process) will be conducted by the surgeon and/or audiologist to inform the candidate about all aspects of the study and evaluation schedule. After reviewing the Informed Consent Form, the candidate will be given the opportunity to review and ask questions about the Informed Consent Form and/or the study prior to signing the Informed Consent Form. The candidate will be offered the opportunity to take the form home to discuss with family members should they choose to do so. If he or she signs the Informed Consent Form, the candidate will then be given a copy of the signed Informed Consent Form to take home.

A candidate will not be considered enrolled until a properly executed Informed Consent Form has been obtained and, along with the results of the pre-operative candidacy evaluation, reviewed and approved by the local Cochlear regional representative (evidenced by the return of a signed study approval form to the investigator).

A pre-operative evaluation will be conducted (pre-operative visit 1, POV1) to provide a baseline (pre-operative) measure of acoustic hearing status, and to document hearing and medical history. Where required, the pre-operative evaluation may occur over multiple clinical sessions. Information collected during the pre-operative session will be recorded on the appropriate case report form (CRF). There will be no pre-determined period required between candidacy and baseline measures. However, candidacy must be re-assessed if more than 90 days have elapsed prior to the surgical date. A hearing and medical history will be obtained and documented during the pre-operative evaluation.

Implant surgery will be conducted (at D0). A video recording will be made during the surgical procedure to enable analysis of the CRT in response to specific surgical events. The video will be made via the operative microscope imaging system during the entire insertion, commencing just prior to cochlear opening and ending after closure of the deep (subcutaneous/muscle) layer. The video will be time-stamped to the CRT recordings. Measures of electrode impedance will be obtained during the surgery. At the completion of each subject's surgical procedure a questionnaire will be completed by the surgeon to document aspects of the surgical procedure (including surgical approach, administration of corticosteroids, and ease and depth of electrode insertion).

Post-operative assessment at 4-6 weeks (+/- 1 week) post-activation and 3 months (+/- 2 weeks) post-activation will be conducted, and involve a series of clinical tests including otoscopy, audiometry, tympanometry and electrode impedance assessment. At either 4-6 weeks post-surgery (+/- 1 week), or 3 months (+/- 2 weeks) post-activation, post-operative CRT will also be conducted.

If an intra-or post-operative imaging is performed as part of the routine clinical management at participating site, that data will be analyzed to provide an estimate of electrode array position.

Medical and audiological care throughout the clinical investigation, and at the conclusion of the investigation, will be as per standard clinical protocol for each investigational site, with the exception of the additional measurements taken as outlined.

7.3 Procedures

7.3.1 Audiometric Thresholds and Tympanometry

Unaided audiometric thresholds will be obtained for each ear, with insert earphones, using the standard audiometric technique for pure-tone air-conduction testing. All pre- and post-implantation testing will be completed using a clinical audiometer calibrated to appropriate standards. Pure tone threshold exploration will be completed using the adaptive Hughson & Westlake procedure (1944).

As these subjects have measurable low-frequency hearing, it is important that appropriate consideration be made for masking (procedure outlined in Appendix A).

Testing for both ears will include the following:

- Air conduction thresholds: 125, 250, 500, 750, 1000, 1500, 2000, 3000, 4000, 6000, 8000 Hz;
- Bone conduction thresholds: 250, 500, 750, 1000, 1500, 2000, 3000, 4000 Hz;
- Tympanometry in each ear

Note that responses to pure-tone stimuli presented will need to be confirmed as an auditory ('heard') versus vibrotactile ('felt') response and recorded accordingly.

7.3.2 Surgical Preparation

Preparation for surgery will occur as per standard clinical procedures and following recommendations in the Cochlear Response Telemetry Research Tool User Guide to ensure the sterile field is not compromised. The surgical team must take necessary precautions during preparation to ensure that fluid has not flooded the external ear canal, since that might influence the delivery of the acoustic stimulus to the cochlea. The surgical team must ensure that the drapes are thin and not doubled over at the site where the external coil will be magnetically coupled with the receiver-stimulator.

Video recording of all surgeries is required, to enable analysis of the CRT in response to specific surgical events. The video will be made via the operative microscope imaging system during the entire insertion, with recording to commence just prior to cochlear opening and ending after closure of the deep (subcutaneous/muscle) layer. The video will be time-stamped to the CRT recordings.

7.3.3 Surgery

Surgery will be conducted as per each surgeon's standard clinical practice. No feedback will be provided to the surgeon as to the status of the cochlear microphonic during insertion.

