5.6 Risk mitigations

The investigators or qualified delegates will conduct the CRT measurements and will be trained in the use of the software and associated hardware system prior to commencement of the investigation.

All investigators will be informed in advance of the following potential hazards and mitigations associated with use of the investigational device or investigation procedure:

- a) All supplied CRT equipment is provided non-sterile. Therefore the Freedom processor, RF coil and programming cable must be placed in a sterilized bag for all intra-operative measures. The insert foam tip and tubing used to deliver the acoustic stimulus, and all other non-sterile equipment must be isolated from the sterile field.
- b) It is important to ensure that the correct routine (intra-operative or post-operative) be selected in the software to avoid risk to overly loud and/or non-auditory percept being elicited through inappropriate use of the intra-operative conditioning parameters during the post-operative visits. The software will provide a warning on initiation of the intra-operative routine to minimize the risk of inappropriate use of this routine post-operatively.
- c) It is important that the equipment used as part of the CRT research tool must not be connected to mains power or a mains powered accessory during all testing.
- d) The surgeon will use his/her discretion as to the acceptable extension to the operating time for each individual, and will terminate use of the CRT tool as needed.

Pre-operative, peri-operative and post-operative use of concomitant medications will be documented for each subject. Use of glucocorticoids will follow each surgeon's and investigational site's standard clinical protocol.

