7.3.4 Intra-Operative Cochlear Response Telemetry Recording and Surgical Video

Intra-operative video recording will be obtained prior to cochlear opening and conducted during electrode insertion and until the closure of the subcutaneous/muscle layer.

After the receiver-stimulator package is positioned and secured, the transmitting coil and sound processor will be placed in a sterile sleeve or bag and subsequently the coil magnet placed in position over the implant package. Electrode conditioning will be conducted when the most apical electrode (electrode 22) is first placed into the basal turn of the cochlea, just prior to advancement of the array, or in a saline solution prior to insertion. On the stabilization of the impedance of the apical electrode, the surgeon will be informed that the insertion may commence. Intra-operative recordings obtained during electrode insertion will typically use a 500 Hz acoustic stimulus (of 6 ms duration and an inter-

stimulus interval of 70 ms) presented at 100 dB HL, with recording on the most apical electrode (electrode 22).

The surgical video will be time-stamped to the CRT recordings. This will be achieved with the surgeon clicking surgical tweezers in front of the microscope 3 times at the end of the surgery, whilst the operator records the current index on the CM monitoring trace that will be updating in real-time. The operator of the CRT software will also capture surgical events using the software time-stamped to the CM recording.

Monitoring of the CM will continue throughout the surgical procedure until closure of the deep (subcutaneous/muscle) layer.

Post-insertion measures will be obtained (after closure of the subcutaneous/muscle layer) using a frequency sweep and an electrode sweep routine.

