7.6 Monitoring Plan

The study will be monitored for data quality, and adherence to ISO14155 or equivalent FDA guidelines and regulatory requirements as outlined in the study monitoring plan. Site initiation and training will be provided to ensure that study site personnel understand the protocol and schedule of activities, mechanics of the study device, study staff responsibilities, data capture and regulatory requirements. Due to the short nature of the study, Interim Monitoring activity (remote or on-site) will be completed once a site completes a multiple of 5 study subjects (i.e., after 5, 10, 15 etc. subjects are completed) or in the event of protocol compliance or GCP concerns. Completed CRT data will be collated and reviewed by the Sponsor throughout the duration of the study, to ensure that data collection is complete and consistent with the requirements of the investigation. The study close-out effort will be conducted at the conclusion of the site's participation in the study.

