8 STATISTICAL CONSIDERATIONS

The primary hypothesis will be tested with a between-groups t-test or non-parametric Mann-Whitney U test using a one-sided alpha level of 0.05. This analysis will compare group mean low frequency postoperative hearing deterioration at FUV1 in the implanted ear for subjects with compromised CM compared to subjects with preserved CM. Compromised CM will be defined as a CM with an irreversible reduction in amplitude during surgery; specifically a $\geq 30\%$ reduction in maximum CM amplitude that does not recover to within 10% of the maximum amplitude. Preserved CM will be defined as a CM with $< 30\%$ amplitude reduction at any point during the surgery. Subjects not falling into the compromised or preserved CM groups will not be included in the analysis. The mean or median threshold drop for the CM compromised and CM preserved groups will be separately calculated as the mean or median of individual subjects' low frequency deterioration (4-6 week post-surgery threshold minus pre-operative threshold in the implanted ear) for the corresponding CM group. For each subject, the low frequency deterioration will be calculated as the average deterioration across the frequencies 500 Hz, 750 Hz and 1000 Hz, where there is preoperative hearing better than or equal to 80 dB HL in the implanted ear. For example, if a subject's preoperative hearing threshold is better than or equal to 80 dB HL at 500 Hz and 750 Hz but is 90 dB HL at 1 kHz, the hearing deterioration (post-operative threshold minus preoperative threshold) will be computed at 500 Hz and 750 Hz only and then averaged. It is possible that a subject could have hearing deterioration measured at 500 Hz only, if preoperative thresholds at 750 Hz and 1 kHz exceed 80 dB HL. Non-measurable post-operative thresholds will be assigned a value 1 dB above the level at which the limits of the audiometer were reached. Vibrotactile responses will not be included in the analyses.

Sample Size Estimation

Prospective sample size estimation for a two-sample t-test has been conducted, given that the study uses a between-groups design to investigate its primary hypothesis. Specifically, the planned sample size would provide 80% power at the one-tailed 0.05 alpha level to detect at least 15 dB greater deterioration in low frequency acoustic hearing threshold for subjects with compromised CM compared to preserved CM.

The following general assumptions have been made:

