### 3.2.4 Exploratory Hypotheses

The following exploratory hypotheses shall include:

1. *Predictors of the incidence of compromised CM during cochlear implant surgery including influence of electrode type, insertion depth and surgical events*

Descriptive, proportional data will be presented to capture the incidence of the compromised CM for electrode type, electrode array insertion depth and surgical events such as inadvertent moving of the electrode array after insertion completion or during sealing of the round window.

2. *Association of pre-operative high frequency acoustic hearing thresholds with change in latency of CM during electrode array insertion*

It is predicted that greater CM latency (phase shift expressed in ms) during electrode array insertion will be associated with better pre-operative acoustic high frequency hearing thresholds, will be tested using a Pearson Product Moment Correlation coefficient or Spearman rank correlation coefficient with a one-sided alpha level of 0.025. The CM latency change will be measured between two CM onset points that are as widely spaced as possible, where a preserved CM is able to be measured as the electrode array is advanced into the cochlea (e.g. 10th electrode to enter versus the 22nd electrode). This CM onset range for the latency change measurement will be identical for all subjects. It will be selected by analysing the group CM data to 1) be sufficiently wide so that the latency measure is sensitive to the potential influence of surviving hair cell populations along the basilar membrane that respond to a range of frequencies and 2) include enough subjects to have adequate power for the primary endpoint analysis. Greater CM latency change will be represented by higher numbers. Pre-operative high frequency hearing will be defined as the average of pre-operative hearing thresholds in the implanted ear at 2 kHz, 3 kHz and 4 kHz, with lower numbers representing better high frequency hearing. Therefore, a negative correlation is predicted by the alternative hypothesis.

3. *Investigation of the influence of demographic and surgical factors on the morphology and time-course of the CM response during insertion and post-operatively.*

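### Masking to the CM result is incompletely specified: the surgeon rule has an ambiguous end point, and nothing masks the follow-up audiologist or whoever assigns the CM groups

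*Protocol*

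**What the plan says.** **Surgeon.** Protocol 7.3.3: "No feedback will be provided to the surgeon as to the status of the cochlear microphonic during insertion". The same section leaves surgery to each surgeon's standard practice.

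**Exposure window.** Protocol 7.3.4: "Monitoring of the CM will continue throughout the surgical procedure until closure of the deep (subcutaneous/muscle) layer". Protocol section 8 defines preserved CM as less than 30% "amplitude reduction at any point during the surgery", and SAP 3.2.2 uses the same span. SAP 3.2.4 item 1 lists "surgical events such as inadvertent moving of the electrode array after insertion completion or during sealing of the round window" among the events of interest.

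**Who sees the trace.** Protocol 5.6: "The investigators or qualified delegates will conduct the CRT measurements". At the end of surgery the surgeon gives a visual time mark "whilst the operator records the current index on the CM monitoring trace that will be updating in real-time" (Protocol 7.3.4). The surgeon then completes a questionnaire covering ease and depth of insertion (Protocol 7.2, 7.3.7).

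**Outcome.** Thresholds come from a manual adaptive procedure in which "responses to pure-tone stimuli presented will need to be confirmed as an auditory ('heard') versus vibrotactile ('felt') response" (Protocol 7.3.1). Felt responses are left out of the analysis (Protocol section 8, SAP 3.2.2). Post-operative CRT takes place at FUV1 or FUV2, both of which include audiometry (Synopsis schedule, Protocol 7.2). Neither the order of the two tests nor a separation of staff is stated.

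**Classification.** Protocol 7.6: "Completed CRT data will be collated and reviewed by the Sponsor throughout the duration of the study". The sample-size text in Protocol section 8 refers to a blind, but only to say that CM-group counts can be reviewed without seeing outcomes by group. SAP section 5 records that the compromised-CM definition was modified in V3.

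**The concern.** The primary comparison sets an exposure read from a live trace against an outcome obtained by a person running a behavioural test. Three people could let knowledge of one affect the other.

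- **The surgeon.** If the masking window is shorter than the exposure window, a drop seen during sealing or closure could become known before the operation ends or the questionnaire is filled in. Protocol section 4 itself says that near real-time feedback might lead surgeons to modify technique.
- **The audiologist.** The person who watched the trace may also test at FUV1, or may record post-operative CRT just before the audiogram.
- **The classifier.** Nothing requires the CM group to be fixed before hearing results are seen.

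With one primary test at one-sided 0.05, a small systematic difference in how the two groups are handled or measured would act directly on the estimated contrast.

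**Working it through.** **1. Is the surgeon rule narrower than the exposure window?** The uses of the term, side by side:

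| Place | Where insertion appears to end |
|---|---|
| Protocol 7.2 and 7.3.2 (video) | After deep-layer closure: the recording of the entire insertion runs to that point |
| Protocol 7.3.4, last paragraph | At closure: post-insertion measures come after it |
| Protocol 7.3.4, first paragraph | Before closure: recording covers insertion and then continues until closure |
| SAP 3.2.4 item 1 | Before sealing and closure: events after insertion completion are named |

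On the first two readings the rule covers the monitored period. On the last two it stops short. The text does not settle which is meant.

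**2. Is anyone else masked?** Protocol 5.6, 7.2, 7.3.1, 7.3.8, 7.6 and 8 and SAP 3.2.2 to 3.6 contain no masking rule for the audiologist or the CM classifier. Appendix A concerns masking noise in audiometry, not blinding.

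**3. What could a differential shift do?** Inputs from Protocol section 8 and SAP 3.1: SD 25 dB, difference 15 dB, one-sided alpha 0.05, power 0.80, 36 per group before inflation, 41 and then 43 after it.

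Formula: with n per group, SE = 25 × √(2/n) and df = 2n − 2. The rejection probability at a mean difference d is P(T > t₀.₉₅,df), where T is noncentral t with noncentrality d/SE.

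*The plan's own figure.* At n = 36, SE = 25 × √(2/36) = 5.89 and noncentrality = 15/5.89 = 2.55, so power is 0.809. At n = 35 power is 0.7996. The stated 36 per group is reproduced.

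*Illustration.* The true difference is 0, and a shift b is added to one group only. The documents give no value for b, so every value is an assumption. The 5 dB value equals one tone step in Appendix A, which is a step size and not evidence of a mean shift.

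| b (dB) | Type I error, n = 36 | Type I error, n = 43 |
|---|---|---|
| 0 | 0.050 | 0.050 |
| 1 | 0.070 | 0.072 |
| 2.5 | 0.110 | 0.118 |
| 5 | 0.211 | 0.234 |

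For n = 43, SE = 25 × √(2/43) = 5.39. A shift of the opposite sign would lower power instead: if 15 dB became 12 dB, power would fall from 0.809 to 0.645 at n = 36 and from 0.868 to 0.713 at n = 43. The 3 dB loss is also an assumption.

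**The case against.** Much of the case on the other side stands.

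- **The surgeon rule may already reach closure.** Protocol 7.2 and 7.3.2 support that reading. A reader might infer that the operator is free to report a drop once the array is in. The mixed usage does not support so definite a reading; the defect is an ambiguity.
- **Care prompted by the CM would already depart from the plan.** Protocol 5.1, 7.2 and 7.3.3 keep surgery and management standard, and section 11 bars deviations outside emergencies. A reader might also infer that any such effect could never be separated afterwards. That goes too far: every operation is videoed and time-stamped to the trace, medication before, during and after surgery is documented (Protocol 5.6), and intra-operative steroids are a named covariate (SAP 3.4.4). These records allow review and adjustment, but they do not keep anyone unaware of the CM.
- **Direction is not established.** It is tempting to say that a tester expecting loss inflates the difference. A response recorded as felt is left out of the analysis, so the call removes a value; if that value was a poor one, measured deterioration shrinks. The subject also gives the response, under a standard procedure.
- **Classification uses a numerical threshold on a stored recording.** That limits discretion but does not remove it. A reader might infer that the V3 definition was changed with hearing results in view. The documents do not say so; SAP 3.2.2 cites a submitted manuscript on the point.

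None of this supplies masking of the audiologist or of the classifier.

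**Conclusion.** The point holds as an unguarded risk, strongest for outcome testing and group assignment and weakest for surgical care. The surgeon rule needs an unambiguous end point. No rule keeps the FUV audiologist unaware of the surgical CM, sets the order of tests at a shared visit, or keeps hearing results from the person assigning groups.

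The size is unknown. Under the plan's SD and test, assumed differential shifts of 2.5 to 5 dB would move a nominal 0.05 error rate to about 0.11 to 0.21 at 36 per group, or 0.12 to 0.23 at 43 per group. These figures show sensitivity only; they do not estimate what happened or will happen. The documents show no actual bias and do not fix its direction. This is a cheap improvement, not a flaw that invalidates the design.

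**What to change.** 1. **Protocol 7.3.3.** Replace the words *during insertion* with *from cochlear opening until the surgeon has completed the surgical questionnaire*, so that masking spans the period over which the CM is classified.
2. **Protocol 7.2.** At each follow-up visit, perform audiometry before any CRT recording and without access to the surgical trace. Where a site already has another audiologist, the person who operated CRT at surgery does not test. Record who tested in every case.
3. **SAP 3.2.2.** Assign CM groups by the stated numerical rule from coded traces, by someone without access to follow-up audiometry, and lock the assignment before merging it with hearing data.

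There is no need to withhold the CM from the whole treating team until FUV2. That could not be met where an investigator runs CRT, as Protocol 5.6 allows.

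**Cost.** Wording changes, a fixed visit order, a tester field and a small coding and locking step; the sample size is unchanged. At single-audiologist sites the tester cannot be separated, so only the visit order and the tester record apply. If visits are already complete, only step 3 can still act.

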7.3.4 Intra-Operative Cochlear Response Telemetry Recording and Surgical Video

Intra-operative video recording will be obtained prior to cochlear opening and conducted during electrode insertion and until the closure of the subcutaneous/muscle layer.

After the receiver-stimulator package is positioned and secured, the transmitting coil and sound processor will be placed in a sterile sleeve or bag and subsequently the coil magnet placed in position over the implant package. Electrode conditioning will be conducted when the most apical electrode (electrode 22) is first placed into the basal turn of the cochlea, just prior to advancement of the array, or in a saline solution prior to insertion. On the stabilization of the impedance of the apical electrode, the surgeon will be informed that the insertion may commence. Intra-operative recordings obtained during electrode insertion will typically use a 500 Hz acoustic stimulus (of 6 ms duration and an inter-

stimulus interval of 70 ms) presented at 100 dB HL, with recording on the most apical electrode (electrode 22).

The surgical video will be time-stamped to the CRT recordings. This will be achieved with the surgeon clicking surgical tweezers in front of the microscope 3 times at the end of the surgery, whilst the operator records the current index on the CM monitoring trace that will be updating in real-time. The operator of the CRT software will also capture surgical events using the software time-stamped to the CM recording.

Monitoring of the CM will continue throughout the surgical procedure until closure of the deep (subcutaneous/muscle) layer.

Post-insertion measures will be obtained (after closure of the subcutaneous/muscle layer) using a frequency sweep and an electrode sweep routine.

